#### **8.4.2.3. *Subject Capacity***

We will ensure each subject's comprehension by asking the subject to explain the basics of the study, including his/her role and the possible risks and benefits after we have walked through the informed consent with him/her. This study will not enroll patients with impaired decision-making abilities.

### **8.5. *Informed consent***

The PI will be responsible for ensuring that valid consent is obtained and documented for all subjects. Consent will be obtained in-person during the enrollment/baseline visit. A member of the treatment team will introduce the research team and obtain permission from the potential subjects to discuss the study and provide information. During the enrollment visit, the research team member will explain the relevant aspects of the study (purpose, relevance, disclosure of risks and benefits) and the subject's role in the study.

#### **8.5.1. *Process of Consent***

The written consent document will embody the elements of informed consent as described in the Declaration of Helsinki and will adhere to the ICH Harmonised Tripartite Guideline for Good Clinical Practice. Informed consent will be conducted before any protocol-specified procedures or interventions are carried out. Informed consent will be obtained in accordance with 21 CFR 50.25 and 45 CFR 46. Information will be presented both orally and in written form.

An investigator or designee will describe the protocol to potential participants in person. The Participant Information and Consent Form may be read to the participants, but, in any event, the investigator shall give the participants ample opportunity to inquire about details of the study and ask any questions before the signing and dating the consent form.

Study staff must inform participants that the trial involves research, and explain the purpose of the trial, those aspects of the trial that are experimental, any expected benefits, all possible risks, the expected duration of the participant's participation in the trial, the procedures of the research study, and the probability for random assignment to treatment groups. Participants will be informed they will be notified in a timely manner if information becomes available that may be relevant to their willingness to continue participation in the trial. They must also be informed of alternative procedures that may be available, and the important potential benefits and risks of these available alternative procedures. Participants and/or legal guardian must receive an explanation as to whether any compensation and any medical treatments are available if injury occurs, and, if so, what they consist of, or where further information may be obtained. Participants and/or substitute decision maker/proxy guardian must be informed of the anticipated financial expenses, if any, to the participant for participating in the trial, as well as any anticipated prorated payments, if any, to the participant for participating in the trial. They must be informed of whom to contact (e.g., the PI or study physician/nurse practitioner) for answers to any questions relating to the research project. Information will also include the foreseeable circumstances and/or reasons under which the participant's participation in the trial may be terminated. The participants and/or substitute decision maker/proxy must be informed that participation is voluntary and that they are free to withdraw from the study for any reason at any time without penalty or loss of benefits to which the participant is otherwise entitled.

Neither the investigators, nor the trial staff, will coerce or unduly influence a participant to participate or continue to participate in the trial. The extent of the confidentiality of the participants' records must be defined, and participants must be informed that applicable data protection legislation will be followed. Participants and/or substitute decision maker/proxy must be informed that the monitor(s), auditors(s), IRB and regulatory authority(ies) will be granted direct access to the participant's medical records for

verification of clinical trial procedures and/or data without violating the confidentiality of the participant, to the extent permitted by the applicable laws and regulations, and that, by signing a written informed consent form, the participant is authorizing such access. Participants and/or substitute decision maker/proxy must be informed that records identifying the participant will be kept confidential, and, to the extent permitted by the applicable laws and/or regulations, will not be made publicly available and, if the results of the trial are published, the participant's identity will remain confidential.

Consent forms are in a language fully comprehensible to the prospective participants. Informed consent will be documented by the use of a written consent form approved by the IRB and signed and dated by the participant or substitute decision maker/proxy and the person who conducted the informed consent discussion. The signature confirms that the consent is based on information that has been provided and all questions have been answered to the prospective participant's satisfaction. Each participant's signed informed consent form must be kept on file by the investigator for possible inspection by Regulatory Authorities and/or the sponsor and Regulatory Compliance persons. The participant should receive a copy of the signed and dated written informed consent form and any other written information provided to the participants, and should receive copies of any signed and dated consent form updates and any amendments to the written information provided to participants.

#### **8.5.2. *Consent Form***

The consent form can be found in the supporting documents.

#### **8.5.3. *Future Use of Stored Specimens***

Any leftover stool specimens will be stored and may be used for future research, under a future protocol, to learn more about DE. These specimens will be stored indefinitely after the study is completed. In the informed consent document, participants will be given an opportunity to choose whether or not their specimens are stored for future use. For participants who choose not to allow storage of their samples for future use, these samples will be destroyed at the end of the study. Data collected during the trial will be coded and stored on secure servers for future research as well. Stored specimens will be provided a unique coded identifier and only [name] research team will be allowed access to the linking data. Any specimens shared with other researchers are to be coded and no linking information shared.

There are no benefits to participants in the collection, storage and subsequent research use of specimens. Reports about future research done with participant's samples will NOT be kept in their health records, but participant's samples may be kept with the study records or in other secure areas. Participants can decide if they want their samples to be used for future research or have their samples destroyed at the end of the study. A participant's decision can be changed at any time before the end of the study by notifying the study doctors or nurses in writing. However, if a participant consents to future use and some of their stool has already been used for research purposes, the information from that research may still be used. If a participant decides they no longer want their specimens stored following the completion of the study, the research team will identify their specimens and destroy them. Any specimens already used for other research purposes or shared with other researchers may still be used.

Up to one gram of stool will be sent to Finch therapeutics for additional analysis. Samples will be de-identified.

#### **8.5.4. *HIPAA***

Information about study subjects will be kept confidential and managed according to the requirements of the Health Insurance Portability and Accountability Act of 1996 ([HIPAA](#)). As part of our consent form is a signed subject authorization form.

The HIPAA identifiers that will be collected for this study include:

- The subjects name
- Race
- Birthdate
- Medical record number

#### **8.5.5. *Revoking Consent***

In the event a subject revokes authorization to collect or use PHI, the investigator, by regulation, retains the ability to use all information collected prior to the revocation of subject authorization. For subjects that have revoked authorization to collect or use PHI, the research will ask permission to at least collect a final stool sample and/or ask final questions regarding the main outcomes of the study.

#### **8.5.6. *Costs to the Subject***

The subject will incur no additional costs to their care by being in this study.

#### **8.5.7. *Payment to the Subjects***

The subjects will be paid \$50.00 upon completion of the study.

#### **8.5.8. *Exclusion of Women, Minorities, and Children (Special Populations)***

Children are excluded for safety reasons.

### **8.6. Early Withdrawals of Subjects**

#### **8.6.1. *Premature Termination of the Study***

In the unlikely event that significant safety concerns arise, the principal investigator can terminate or halt the study pending review by the DMC. In addition, this study may be halted early based on the DMC charter or FDA recommendations. If the study is prematurely terminated or suspended, the PI will promptly inform the IRB and will provide the reason(s) for the termination or suspension.

Circumstances that may warrant termination or suspension include, but are not limited to:

- Determination of unexpected, significant, or unacceptable risk to participants
- Demonstration of efficacy that would warrant stopping
- Insufficient compliance to protocol requirements
- Data that are not sufficiently complete and/or evaluable
- Determination of futility

Study may resume once concerns about safety, protocol compliance, or data quality are addressed and satisfy the sponsor, IRB, DMC, and/or FDA.

#### **8.6.2. *When and How to Withdraw Subjects***

All subjects will be informed during consent that consent is voluntary and they may discontinue participation at any time. If a subject wishes to withdraw from the study, we will ask him/her to contact the study coordinator whose number will be in the enrollment materials.

##### **8.6.2.1. *Data Collection and Follow-up for Withdrawn Subjects***

If the subject is willing, the coordinator will ask to schedule a close-out study visit to collect a final stool sample and follow-up safety evaluation.

A subject may withdraw from the study at any time for any reason with no consequences. A participant

may be withdrawn from the study by the Investigator for the following reasons:

- Adverse event that may make it no longer in the best interest of the subject to continue to participate
- Recurrent *C.diff* infection
- Participant's choice
- Protocol violation/ non-compliance
- Pregnancy
- Lost to follow-up
- Other (must be noted)

The primary reason for withdrawal from the study will be recorded. Participants will be encouraged to complete the Early Termination Visit. The Early Termination Visit procedures are listed in Section 11.4. Although participants are free to withdraw at any time, subjects will be encouraged to remain in the study for follow-up safety evaluation. Every attempt should be made to follow all AEs and SAEs ongoing at the time of early withdrawal to resolution or until stabilized. If possible, a final stool sample will be collected at the time of Early Termination. All subjects who are randomized will be included in the safety analysis.

### **8.7. Participant Confidentiality**

Participant confidentiality is held strictly in trust by the PI, his/her staff, and his/her agents. This confidentiality is extended to cover testing of biological samples in addition to the clinical information relating to participating participants.

The study protocol, documentation, data, and all other information generated will be held in strict confidence. No information concerning the study or the data will be released to any unauthorized third party without prior written approval from the PI.

The PI or delegate and the FDA may inspect all documents and records required including, but not limited to, medical records (office, clinic, or hospital) and pharmacy records for the participants in this study.

## **9. STUDY AGENT**

### **9.1. Description and Formulation**

DE is encapsulated fecal microbiota sourced from human-derived microbes. The human source generating the fecal microbes has been extensively screened for infectious pathogens and microbiome mediated diseases using a standardized process (found in OpenBiome's BBMF # 15543, Section F). Additionally, the capsule delivery vehicle enables *targeted deposition* of the investigational active pharmaceutical ingredient into the colon.

**DE capsules:** The OpenBiome FMT Capsule DE contains frozen human fecal microbiota filtered to 330 microns, theobroma oil, glycerol, hide bovine gelatin, sodium lauryl sulfate, colorants FD&C, and titanium dioxide. The material is contained in a two capsule system: an interior gelatin capsule that houses the drug substance, and an exterior acid-resistant capsule for delivery of the drug substance past the stomach. The product should be stored at -20°C to -80°C. Product expires 6 months after freezing if stored at -20°C.

**Placebo capsules:** Placebo capsules will be identical in appearance to DE capsules but will not have human feces, the active pharmaceutical ingredient. The placebo capsules are filled with Sodium Chloride (0.9%, USP), Glycerol (12.5%, USP) and deionized water to the previously stated volume specification. Capsules are stored frozen at -80°C before dispensing to local site storage. Placebo will be administered the same as the daily arm of the trial.

## 9.2. Packaging and Dissemination

OpenBiome will package the placebo and FMT capsules at their facility. Packaging will be identical and consist of the same saline and glycerol buffer used in FMT processing without the addition of stool. The capsules will be sent to the UW Pharmaceutical Research Center (PRC) to be dispensed.

An inventory will be performed and a drug receipt log filled out and signed by the person accepting the shipment. The designated study staff will count and verify that the shipment contains all the items noted in the shipment inventory. Any damaged or unusable study drug in a given shipment (active drug or comparator) will be documented in the study files.

The site principal investigator (PI) (or designee) will maintain an accurate record of the receipt of the investigational materials as shipped by OpenBiome, including the date received. One copy of this receipt will be returned to OpenBiome when the contents of the investigational materials shipment have been verified. In addition, the unblinded laboratory technician based at the PRC will maintain a log of all clinical trial materials (DE and placebo) dispensed. This clinical trial material accountability record will be available for inspection at any time.

## 9.3. Preparation, Administration and Storage of Study Drug

Produced material will be stored at -80°C and each unit will have a date of production printed on it for tracking purposes. Studies have been conducted to ensure long-term bacterial viability following the freezing process based on studies conducted by Hamilton et al. and Youngster et al. Local site storage at -20°C will be permitted for up to 6 months. Discharged patients will be provided with a kit and instructions on proper at-home storage.

## 9.4. Route of Administration

Participants will undergo administration:

1. Document Review: Confirmation/review of exclusion criteria/contraindications as previously described at baseline.
2. Safety Capsules: Direct observed capsule test, where participants will ingest one inert, size 00 'safety' capsule under direct supervision of the study physician/nurse.
3. Dietary instructions: Patients should fast (clear liquids allowed) for a minimum of 2 hours prior to administration.
4. Capsule administration:
  - a. Patient should ingest the capsules of either FMT or placebo (5 capsules daily or a one-time dose of 30 capsules depending on treatment group) under the direct observation of a physician/nurse while they are admitted.
  - b. Patient should ingest capsules after extraction from freezer, and no longer than 90 minutes after removal.
  - c. Patients should remain fasting (clear liquids allowed) for 1 hour following ingestion but may then return to a full diet.

## 9.5. Prior and Concomitant Therapy/ Standard of Care

We will collect the following information on the patients care during their stay:

- Current medication list
- Antibiotic they are on and dose
- Vital signs at baseline and discharge (taken from medical record): temperature, height, weight, heart rate, blood pressure, O2 saturation if on chronic oxygen therapy.
- Overall assessment of current health

## **9.6. Randomization and Blinding of Study Drug**

Participants meeting the eligibility criteria and willing to consent to the study procedures will be randomized on a 1:1:1 basis with block sizes of 10 to receive one of the following treatments:

1. Daily FMT treatment with 5 capsules/day
2. One-time FMT treatment of 30 capsules
3. Daily placebo (5 capsules/day)

Randomization will be carried out by the UW PRC so that the research team and treatment team remains blinded to whether the patient is receiving FMT or placebo.

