### **7. STUDY DESIGN AND ENDPOINTS**

#### **7.1. General Design**

This is a phase II, double-blind, randomized, placebo controlled trial assessing the effects of either daily (group 1) or one-time (group 2) oral FMT on the composition and function of the gut microbiome compared to placebo (group 3) in a population of patients with a history of CDI currently on antibiotics for a reason other than current CDI. Participants will be 18 years of age or older, have 72 hours or less of an antibiotic and meet all inclusion criteria while having no exclusion criteria prior to randomization. Patients will be randomized at a 1:1:1 ratio using permuted blocks (block size=10). Randomization will be double-blinded. Each subject (n=30) will be followed for 6 months. Stool samples will be taken at baseline and every 3 days  $\pm$  1 day from all subjects regardless of treatment group while the patient is hospitalized. If/when a patient is discharged from the hospital, the patient will continue to provide stool samples every three days during FMT. Following completion of the FMT intervention, the patient will provide stool samples once weekly for the 1 month follow-up period. All patients will be asked to complete a patient diary to report diarrhea history.

Up to one gram of stool will be sent to Finch therapeutics for additional 16s rRNA sequencing.

**Intervention:** There are 2 intervention groups for this study. Both groups will receive oral FMT capsules from OpenBiome for the prevention of CDI during antibiotic treatment. All patients will fast (clear liquids only) for a minimum of 2 hours prior to administration and 1-hour post-administration for the daily groups and be fasting for 8 hours prior and 1 hour post FMT consumption for the single dose group. The capsules will be administered in the patient's room while admitted or in the ID clinic or CRU if the patient is an outpatient and the first dose will occur under direct observation. Patients admitted to the hospital as well as all patients in the single dose group will be observed for 30 minutes post-administration to ensure the capsules are safely consumed. Hospitalized patients need to be observed 30-minutes post-administration following only the first dose. As mentioned above, the oral FMT capsules will be administered in two ways:

**Group 1:** This group will receive daily oral FMT capsules. Five capsules will be administered each day of the

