### **8.3. Exclusion Criteria**

1. Admitted to an intensive care unit (ICU).
2. Females who are pregnant, lactating, or planning to become pregnant during the study. Female patients of childbearing potential will take a pregnancy test at the intervention visit and will be excluded if pregnant.
3. Inability (e.g. dysphagia) to or unwilling to swallow capsules.
4. Known or suspected toxic megacolon and/or known small bowel ileus.
5. Bowel obstruction or other gut motility issues occurring in the last two weeks that are unresolved as noted by the patient or in the EMR.
6. Major gastrointestinal surgery (e.g. significant bowel resection) within 3 months before enrollment not including appendectomy or cholecystectomy.
7. History of bariatric or colectomy surgery.

8. Concurrent intensive induction chemotherapy, radiation therapy, or biologic treatment for an active malignancy. Patients on maintenance chemotherapy may be enrolled after consultation with the medical monitor.
9. Expected life expectancy <6 months.
10. Patients with severe anaphylactic or anaphylactoid food allergy.
11. Solid organ transplant recipients ≤90 days post-transplant or on active treatment for rejection.
12. Neutropenia ( $\leq 500$  neutrophils/mL) or other severe immunosuppression. Anti-TNF will be permitted. Patients on monoclonal antibodies to B and T cells, glucocorticoids, antimetabolites (azathioprine, 6-mercaptopurine, methotrexate), calcineurin inhibitors (tacrolimus, cyclosporine), and mycophenolate mofetil may only be enrolled after consultation with the medical monitor.\*
13. At risk of CMV/EBV associated disease, negative IgG testing for cytomegalovirus (CMV) or Epstein Barr Virus (EBV).
14. Any other gastrointestinal illness including diarrhea.
15. On oral vancomycin or metronidazole.
16. Having been taking the currently prescribed antibiotic for over 72 hours.
17. On an antibiotic treatment anticipated to exceed 19 days.
18. Having received an FMT by any route in the 90 days prior to enrollment.
19. Any condition that would jeopardize the safety or rights of the patient, would make it unlikely for the patient to complete the study, or would confound the results of the study.

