#### **8.4.2.2. *Retention***

Stool samples will be taken from all subjects at baseline and every 3 days  $\pm$  1 day regardless of treatment group while the patient is hospitalized. If/when a patient is discharged from the hospital, the patient will continue to provide stool samples every three days during FMT and once weekly for 4 weeks following FMT. We will call or email the patient weekly until they have completed FMT and once weekly during follow-up to remind him/her to mail us a stool sample and discuss the patient diary. If the patient is receiving either the daily FMT or placebo, we will also remind him/her to be taking his/her capsules as well as ask him/her to count how many pills he/she currently has left for us. If a patient in the one-time FMT group is discharged prior to the FMT consumption time point (48-72 hours post antibiotic treatment completion), he/she will be asked to return to the ID clinic or CRU to receive his/her FMT capsules. Inpatients in the daily and placebo groups will have each dose of 5 capsules observed by a nurse/physician during admission and will be discharged with a cooler containing their FMT capsules and instructed on use. Outpatients in the daily and placebo groups will be asked to come to the ID clinic or CRU to have their first dose observed by a nurse or physician and be given the remaining FMT doses to take home. After discharge, all patients will receive a study brochure tailored to their study arm describing all post-discharge study procedures.

While we will target patients who are on antibiotic doses with a duration of less than 14 days, if a patient's antibiotic regimen exceeds 14 days will be handled in the following manner:

Group 1: Patients will be given the 30 capsule dose of FMT on day 16 or 17 (day 14 + 48 to 72 hours) of antibiotic treatment unless they meet one of the criteria for halting a patient's participation in the study (13.5.2). Participants who are not withdrawn from the study will continue follow-up the same as other patients.

Groups 2 and 3: At 14 days of antibiotics, we will discontinue the daily FMT treatments and patients will move to the weekly follow-up phase of the study unless they meet one of the criteria in section 13.5.2 in which case they will be withdrawn from the study.

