#### *Enrollment: Will take place in a clinical setting*

All patients with a history of CDI on antibiotics for any reason other than CDI meeting the eligibility criteria will be eligible for enrollment. Eligibility will be confirmed during the enrollment visit. Patients admitting with CAP and UTIs will be preferred. A detailed consent process will be administered by study staff who are trained in consenting procedures. Potential participants who fulfill the eligibility criteria will undergo a detailed clinical assessment by the research team which will include demographics, medical history, dietary

information and current medication. Data from this assessment may be from the participant/substitute decision maker, healthcare team and/or medical record.

- Data points at enrollment study visit:
  - General parameters:
    - Date of birth
    - Sex
    - Smoking status
    - Race
    - Ethnicity
    - Highest level of education
  - Past medical history and allergies
    - A focused collection of past medical history (including common infections)
  - Current medication list
    - Current antibiotic use, including dose
  - Dietary history
  - Social history
    - Alcohol, smoking history
  - Recent hospitalizations
  - Exposure to farm animals
  - Recent international travel history
  - Examination findings
    - Vital signs: temperature, height, weight, heart rate, blood pressure, O2 saturation if on chronic oxygen therapy. (Vital signs measurements at all time points may be abstracted from medical records if available.)
    - Relevant review of symptoms
  - Overall assessment of current health
  - Stool consistency (Bristol Stool Scale) and frequency
- Sample collection
  - Stool sample collected using a stool collection kit/hat and provided with patient diary
- Formal aspects
  - Informed consent procedure
  - Verification of inclusion and exclusion criteria including administering 'test' capsule and documenting:
    - Safe to receive intervention (yes/no)
    - Able to swallow test capsule (yes/no)

Immunocompromised patients at risk for CMV/EBV will have blood drawn for the EBV and CMV antibody test done by the UWHC lab. The blood draw will be done by a UWHC phlebotomist or their local lab if this is preferred by the patient. All costs will be covered by the study. Results will be released to the patient and included in their medical record.

*Baseline (Day 0): Will take place in a clinical setting*

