After the baseline clinical assessment and stool sample have been collected, subjects in groups 1 and 3 (daily FMT and daily placebo) are eligible to undergo administration of the intervention (DE or placebo) in

accordance with the randomization schedule. The intervention will be administered by the blinded treatment staff and the participant observed for 30 minutes following administration. Post-ingestion observation of inpatients will only occur after the first dosing; subsequent inpatient dosing will be administered by a study physician/nurse but do not require 30 minutes of observation. Pre-intervention vital signs (as previously described) will be collected or abstracted from the medical record prior to first dose. Participants will be provided with information regarding monitoring for minor and severe adverse event related to the intervention administration. Participants will be encouraged to report any concerning symptoms to staff. Oral nutrition may commence 1 hour post-capsules administration. Study staff do not need to collect a blood sample to check for neutropenia prior to dosing.

For all patients, a baseline stool sample will be collected and all patients should begin to fill out their patient diary starting on Day 0. If a patient is unable to provide a stool sample, peri-rectal swabs may be collected.

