### **12. STUDY ANALYSIS**

#### **12.1. Sample Size**

A total of 30 subjects – 10 per treatment group – will be recruited into this study. As this is a pilot study, sample size was not driven by a statistical test of hypotheses, instead it was driven by a pool of available patients eligible and willing to participate.

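### With a printed fixed block of 10 and a visible single-dose arm, recruiting staff could be certain of the regimen type of about 2 to 4 of the 30 next patients

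*Combined protocol and SAP*

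**What the plan says.** **Allocation.** Section 7.1: "Patients will be randomized at a 1:1:1 ratio using permuted blocks (block size=10". Section 9.6: "will be randomized on a 1:1:1 basis with block sizes of 10 to receive one of the following treatments". Neither mentions varying sizes or stratification, or says how ten places are divided among three arms. Section 12.1 gives the totals: "A total of 30 subjects – 10 per treatment group – will be recruited into this study". The Pharmaceutical Research Center runs the randomization. The aim stated in 9.6 is to keep the research and treatment teams blind to FMT versus placebo; masking of the regimen is not claimed.

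**What staff can see.** In Section 11.1, Baseline (Day 0), "subjects in groups 1 and 3 (daily FMT and daily placebo) are eligible to undergo administration of the intervention (DE or placebo". Under Section 11.2 the single-dose group takes its 30 capsules 48-72 hours after antibiotics end. Section 7.1 describes placebo only as five capsules a day, so the single-dose arm has no daily dummy and no 30-capsule placebo counterpart. Section 8.4.2.2 adds that "all patients will receive a study brochure tailored to their study arm", and that callers ask only daily-arm patients for capsule counts.

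**Where judgment enters.** Exclusion 19 in Section 8.3 covers any condition that "would make it unlikely for the patient to complete the study". The medical monitor is consulted on several immunosuppressed groups. Section 11.1 says "Patients admitting with CAP and UTIs will be preferred".

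**The concern.** Blinding of capsule contents and concealment of the next assignment are separate protections. Identical capsules give the first for daily FMT versus daily placebo. They do not hide whether a patient is single-dose or daily, and a known fixed block lets that information accumulate. Once the single-dose places in a block are used up, every remaining patient in it must be daily. If only single-dose places remain, each must be single-dose.

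The regimens differ in burden: 30 capsules at one supervised sitting, with a return visit for anyone already discharged, against five capsules a day, largely at home after discharge. A recruiter who knows the next regimen could, even without meaning to, let it affect a judgment about likely completion or the order of two candidates. With 10 per arm, two steered patients are 2/10 = 20% of an arm. A resulting difference in frailty, antibiotic type or likelihood of completing could look like a regimen effect on microbiota, CDI, safety or retention. Retention by group is itself an outcome in Section 7.2.2.

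**Working it through.** The plan states no predictability figure, and Section 12.1 says "sample size was not driven by a statistical test of hypotheses", so there is no figure of the plan's own to reproduce.

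**Inputs.** Block size 10 (7.1, 9.6); 30 patients, 10 per arm (12.1), hence 10 single-dose and 20 daily. Since 10 = 3 × 3 + 1, no block of 10 can be exactly 1:1:1. *Assumption:* each block is 4:3:3 with the extra place rotating, so the three blocks hold 3, 3 and 4 single-dose places in some order. *Assumption:* staff see each past patient's regimen type before the next enrollment.

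**Formula.** In a randomly ordered block of n with k single-dose places, the expected number of daily patients after the last single-dose patient is (n − k)/(k + 1). The expected number of single-dose patients after the last daily one is k/(n − k + 1). Their sum is the expected number of certain assignments.

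- k = 3: 7/4 + 3/8 = 2.125
- k = 4: 6/5 + 4/7 = 1.771
- Composition of every block known: 2 × 2.125 + 1.771 = 6.02 of 30
- One list of 30 with k = 10: 20/11 + 10/21 = 2.29 of 30

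**Composition not known.** By simulation, an assignment counts as certain only if every block composition consistent with the history gives the same type.

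| What staff know | Certain, of 30 (5th-95th percentile) | Correct best guesses, of 30 |
|---|---|---|
| 3 or 4 single-dose places per block; total of 10 not used | 1.9 (0-5) | not needed here |
| 4:3:3 split and total of 10 per arm | 3.9 (1-8) | 21.4 |
| Composition of each block | 6.0 (3-10) | 21.8 |
| One permuted list of 30, total used | 2.3 | 20.8 |
| Random sizes 6/9/12/15 | 0.3 (total of 30 not used) to 2.3 (used) | about 21.3 to 21.5 |

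Always guessing daily is right 20.0 times in 30. In the second row the third block matters most. Once two blocks are complete, the total of 10 reveals its composition, and it contributes (2 × 2.125 + 1.771)/3 = 2.0 certain assignments on average.

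**Visibility lag.** With composition known, the 6.0 falls to 3.0 if the newest patient's regimen is not yet seen, and to 1.5 if the newest two are not. Thirty patients over one year is about one every 365/30 = 12 days, while the regimen shows at about Day 0-1, so a long lag is unlikely.

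**The case against.** **Size.** A reader might infer that the printed block size lets staff know 4 to 6 of 30 assignments for certain. The documents do not support that. The 6 requires knowing which block holds four single-dose places, and that stays with the Pharmaceutical Research Center. Even the 3.9 needs an assumed split and use of the arm totals. This objection stands.

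**Gain from the fix.** Best-guess accuracy moves little: 21.4 to 20.8 with one list, and hardly at all with random blocks. It can also be said that 1.9 certain assignments now is no worse than 2.3 with one list. Those two figures assume different knowledge, though. The 2.3 requires use of the arm total. For staff who use it, the comparison is 3.9 against 2.3. For staff who do not, a single list gives no certain assignments, because nothing tells them when the places run out.

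**Analysis.** A reader might infer that nothing in the analysis would correct an imbalance. That is too absolute. Section 2 names ANCOVA and linear mixed models, every patient gives a baseline sample, and antibiotic and dose are recorded. However, no covariates are named and Section 12.3 sets out no adjustment. Unmeasured frailty or likelihood of completing would remain.

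**Opportunity.** Two eligible candidates within the same 72 hours will be uncommon at one enrollment per 12 days, and patients are scarce. The CAP/UTI preference is tied to short antibiotic courses and applies to all arms. Sections 7.1, 8.1 and 9.6 already place eligibility before randomization, so that control is not missing, although it does not stop prediction. That eligibility assessors also track regimens is inferred from a single-site team with no stated separation of roles. These points reduce the risk without removing it.

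**Conclusion.** The point holds as a concealment weakness of modest size. Under an assumed 4:3:3 split, with past regimens visible, about 2 to 4 of 30 regimen types could be known with certainty before enrollment (1.9 to 3.9 on average), and about 6 only if block composition became known. The certain cases matter most, because there a recruiter's expectation cannot be wrong.

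Two of the three pairwise comparisons are exposed to possible selection bias: single-dose versus placebo and single-dose versus daily FMT. Baseline adjustment would address only part of it. A reader might go further and infer that the FMT-versus-placebo blind fails, or that patients will be steered. Neither follows: identical capsules keep daily FMT and daily placebo masked from each other, and the documents show an opportunity, not conduct. In a pilot without a power-based sample size, this is a minor to moderate improvement worth making because it is cheap.

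**What to change.** In Sections 7.1 and 9.6, replace the fixed block of 10 with a 1:1:1 list generated and held by the Pharmaceutical Research Center, in one of two forms:

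- one permuted list of 30 (10:10:10), with about 2.3 certain assignments and 20.8 correct best guesses; or
- randomly ordered block sizes that are multiples of 3. For 6/9/12/15 this gives about 0.3 to 2.3 certain assignments, depending on whether staff use the total of 30, with little change in best-guess accuracy.

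Either form also removes the problem that 10 does not divide by three. Keep block details out of the protocol given to recruiting staff and in a document held by the Pharmaceutical Research Center.

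The cost is a wording amendment and a new list from a unit that already runs the randomization. The single list has one small downside: looser balance over time if enrollment stops early. No regimen or visit changes.
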